2.7.2 Deaths

All deaths (on-treatment death and post-treatment death) will be summarized. Separate summaries for on-treatment and all deaths (including post-treatment death) will be produced system organ class and preferred term.

All deaths will be listed using Safety set. All deaths those collected during the pre-treatment and post treatment period will be flagged. A separate listing of deaths prior to starting treatment will be provided for all screened subjects.

2.7.3 Laboratory data

On analyzing laboratory values, data from all sources (central and local laboratories) will be combined as per Section 8.3.2 of the protocol. The summaries will include all assessments available for the lab parameter collected no later than 105 days after the last study treatment administration date. Following lab parameters will be analyzed :

Table 2-1

Test category	Test name
Hematology	Hematocrit, Hemoglobin, MCH, MCHC, MCV, reticulocytes (%), Platelets, Red blood cells, White blood cells, RBC Morphology, Differential (Basophils, Eosinophils, Lymphocytes, Monocytes, Neutrophils, Bands, Other
Chemistry	Alkaline phosphatase, ALT, AST, Gamma-glutamyl transferase (GGT), Lactate dehydrogenase (LDH), Bicarbonate, Calcium, Magnesium, Phosphorus, Chloride, Sodium, Potassium, Creatinine, Creatine kinase, Direct Bilirubin, Indirect Bilirubin, Total Bilirubin, Total Cholesterol, LDL, HDL, Total Protein, Triglycerides, Blood Urea Nitrogen (BUN) or Urea, Uric Acid, Amylase, Lipase, Glucose (non-fasting), estimated glomerular filtration rate (eGFR).
Urinalysis	Macroscopic Panel (Dipstick), done locally: Color, Bilirubin, Blood, Glucose, Ketones, Leukocytes esterase, Nitrite, pH, Protein, Specific Gravity, Urobilinogen Microscopic Panel (performed if dipstick is positive): Red Blood Cells, White Blood Cells, Casts, Crystals, Bacteria, Epithelial cells Urine creatinine/protein ratio, Microalbumin
Coagulation	Prothrombin time (PT) , International normalized ratio [INR]), Activated partial thromboplastin time (APTT)
Hepatitis markers	HBV-DNA, HbsAg, HbsAb, HbcAb, HCV RNA-PCR, HCV Ab
Additional tests	HIV Ab

For results reported by the central laboratory, continuous hematology and chemistry results will be summarized descriptively in SI units at each scheduled time point. Visits summaries will include baseline and post baseline visits, including early termination and Follow-Up. Changes from baseline will also be summarized at each time point.

The following summaries will be produced for laboratory data by laboratory parameters:

Separate summaries of change from baseline for each lab test category.

- Worst post-baseline CTCAE grade (regardless of the baseline status). Each subject will be counted only once for the worst grade observed post-baseline.

- Shift tables using CTCAE grades to compare baseline to the worst on-treatment value; for laboratory tests where CTCAE grades are not defined, shift tables using the low/normal/high/(low and high) classification to compare baseline to the worst on-treatment value.

The following listings will be produced for the laboratory data:

- Listings of all laboratory data, with CTCAE grades and classification relative to the laboratory normal range. Lab data collected during the post-treatment period will be flagged.
- Listing of all CTCAE grade 2, 3, or 4 laboratory toxicities.

Coagulation parameters will be summarized descriptively at each time-point. Changes from baseline will also be summarized.

Urinalysis results will be listed in individual subject data listings only. In addition, a listing containing individual subject hematology, chemistry, and coagulation values outside the reference ranges will be provided. This listing will include data from scheduled and unscheduled time points.

Hepatitis markers and additional tests only performed at screening will be summarized and listed.

Urine creatinine/protein ratio will be summarized descriptively at screening visit 3 and EoT visit, and summary of change will be presented.

2.7.4 Other safety data

2.7.4.1 ECG and cardiac imaging data

Standard 12-lead ECG will be performed (in the supine position) after the subject has been resting for 5-10 min prior to ECG assessments.

A standard 12 lead ECG will be performed

- at screening
- at the end of treatment

When ECG triplicates are collected at any assessment, the average of the ECG parameters at that assessment will be used in the analyses.

12-lead ECGs including PR, QRS, QT, QTcF and HR intervals were obtained for each subject during the study. ECG data was read and interpreted centrally.

The number and percentage of subjects with notable ECG values will be presented at screening visit and EoT visit. In addition, a listing of these subjects will be produced.

- QT, QTcF
 - New value of > 450 and ≤ 480 ms
 - New value of > 480 and ≤ 500 ms

- New value of > 500 ms
- Increase from baseline of > 30 ms to ≤ 60 ms
- Increase from baseline of > 60 ms
- HR
 - Increase from baseline >25% and to a value >100 bpm
 - Decrease from baseline >25% and to a value <50 bpm
- PR
 - Increase from baseline >25% and to a value >200 ms
 - New value of >200 ms
- QRS
 - Increase from baseline >25% and to a value >120 ms
 - New values of QRS >120 ms

For cardiac imaging data, left ventricular ejection fraction (LVEF), mean pulmonary arterial pressure (mPAP), and tricuspid regurgitation jet velocity (TRV) will be summarized at screening and end of treatment visit. In addition, all data will be listed.

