### **8.3.5 Cardiac assessments**

#### **8.3.5.1 Electrocardiogram (ECG)**

Standard 12-lead ECG will be performed (in the supine position) after the subject has been resting for 5-10 min prior to ECG assessments.

A standard 12 lead ECG will be performed

- at screening
- at the end of treatment

Additional, unscheduled, safety ECGs may be repeated at the discretion of the investigator at any time during the study as clinically indicated. Unscheduled ECGs with clinically significant findings should be collected in triplicate. Local cardiologist ECG assessment may also be performed at any time during the study at the discretion of the investigator.

Interpretation of the tracing must be made by a qualified physician and documented on the ECG CRF page. Each ECG tracing should be labeled with the study number, subject initials (where regulations permit), subject number, date, and kept in the source documents at the study site.

Clinically significant ECG abnormalities present at screening should be reported on the Medical History CRF page. New or worsened clinically significant findings occurring after informed consent must be recorded on the Adverse Events CRF page.

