#### **12-Lead ECG**

12-lead ECGs including PR, QRS, QT, QTcF and HR intervals will be obtained for each subject during the study. ECG data will be read and interpreted locally.

The number and percentage of subjects with notable ECG values will be presented. In addition, a listing of these subjects will be produced.

[figure not shown]
Notable/abnormal values for safety data will be further specified in the RAP.

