2.1 Data analysis general information

The data will be analyzed by Novartis and/or a designated contract research organization (CRO) (if applicable). It is planned that the data from all centers that participate in this protocol will be used for analysis. Analysis datasets and statistical outputs will be produced using the most recent SAS® Version 9.4 (SAS Institute Inc., Cary, NC, USA), and stored in Novartis global programming & statistical environment (GPS).

General analysis conventions

Descriptive statistics for continuous variables will include number of subjects (n), mean, standard deviation (SD), minimum, lower quartile (Q1), median, upper quartile (Q3), maximum. Summary statistics for discrete variables will be presented in the number and percent of subjects in each category. Summary statistics will also be presented graphically wherever applicable.

If not otherwise specified, p-values and confidence interval (CI) will be presented as two-sided. Unless otherwise stated, the default level of significance will be set to 5%.

For categorical data, percentages will be rounded up to one decimal place. For continuous data, mean, and median will be rounded up to one additional decimal place compared to the original data. Standard deviation will be rounded up to two additional decimal places. Minimum and maximum will be displayed with the same accuracy as in the original data. Wherever changes from baseline will be used, change will be calculated as “post-baseline value – baseline value”. The number of decimal places for the “change from baseline” variables will be the same as for the original measurement.

The analysis will be conducted on all subjects' data at Week 26 and at the time, the trial ends (Week 52).

Unscheduled assessments

The following points summarize the rules for unscheduled assessments:

- All unscheduled assessments at the baseline before the first dose should be included for consideration when calculating the baseline value.
- In summary tables by visit, unscheduled assessments should not be included unless they qualify as baseline.

- In shift and abnormality tables, all unscheduled assessments are included.

Unscheduled assessments will be reported along with the scheduled assessments in the listings.

Data included in analysis

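### SAP 2.7.4.1 may leave unscheduled on-treatment ECGs out of the notable-value table, against one of its own general rules, and it contradicts the protocol on who read the ECGs

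*SAP*

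**What the plan says.** **Schedule.** Protocol 8.3.5.1 lists two planned 12-lead ECGs, one at screening and one "at the end of treatment". Beyond these, "Additional, unscheduled, safety ECGs may be repeated at the discretion of the investigator at any time during the study as clinically indicated". It adds: "Unscheduled ECGs with clinically significant findings should be collected in triplicate".

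**Table.** Protocol 12.6.2 says "The number and percentage of subjects with notable ECG values will be presented" and stops there. SAP 2.7.4.1 adds a limit: "The number and percentage of subjects with notable ECG values will be presented at screening visit and EoT visit". The SAP then gives thresholds for QT and QTcF, heart rate, PR and QRS, and asks for a listing of the subjects concerned. It also says that triplicates from any assessment are averaged for the analyses.

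**General rule.** SAP 2.1 has three relevant conventions for unscheduled assessments. By-visit summary tables leave them out unless they serve as baseline. For abnormality tables the rule is the reverse: "In shift and abnormality tables, all unscheduled assessments are included". Listings show them in either case.

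**Reader.** SAP 2.7.4.1: "ECG data was read and interpreted centrally". Protocol 12.6.2: "ECG data will be read and interpreted locally".

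**The concern.** Unscheduled safety ECGs are the ones taken because somebody had a reason to look. If the notable-value table is built strictly on the screening and EoT visits, a QT, PR or QRS finding seen on such a tracing between infusions never enters the count, and a subject whose EoT tracing is unremarkable appears clean. The protocol's own wording for the table does not have this effect.

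The reader statement is a separate matter. SAP section 1 says that departures from the protocol are documented and that the SAP text will be updated for entry into the clinical study report. Uncorrected, the report would describe a central read that the protocol does not provide for.

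**Working it through.** No sample size, power or error rate is involved. The check is a count of the schedule and a side-by-side reading.

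1. **Dosing visits** (Protocol Table 6-1): Weeks 1 and 3, then every 4 weeks from Week 7 to Week 51. The second run has (51 − 7)/4 + 1 = 12 visits, so there are 2 + 12 = 14 in all.

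2. **Scheduled ECGs** (Protocol 8.3.5.1): one before dosing and one at end of treatment, which Protocol section 8 places 2 weeks after the last infusion (Week 53, target Day 365 in the SAP visit-window table). For a subject who completes dosing, the 14 infusion visits have 0 scheduled ECGs. Every tracing between first and last infusion in such a subject is unscheduled. (The ECG row of Protocol Table 8-1 is not readable in the text available, so the schedule rests on 8.3.5.1.)

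3. **Which SAP 2.1 rule applies?** The table in 2.7.4.1 counts abnormal values, so the abnormality-table rule brings unscheduled ECGs in. It is also presented by visit, so the by-visit rule takes them out. The two rules give opposite instructions for one table. The specific sentence in 2.7.4.1 names visits, which leans toward exclusion. The averaging of triplicates leans toward inclusion, because the only triplicates the protocol asks for are unscheduled ones.

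4. **Do visit windows settle it?** No. SAP 2.1.1 applies them to vital signs, laboratory and PRO assessments and does not name ECGs.

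5. **What is still counted?** SAP 2.1.1 defines the on-treatment period as first dose to 105 days after the last dose, or to the EoT date for subjects who move to commercial supply. The EoT ECG falls inside it and is in the table under either reading.

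6. **Screening column.** The criteria number 5 for QT/QTcF, 2 for heart rate, 2 for PR and 2 for QRS: 5 + 2 + 2 + 2 = 11. Each is a new value or a change from baseline. The safety baseline in SAP 2.1.1 is the last assessment on or before the start of treatment, which is normally the screening ECG. It cannot be new or changed relative to itself, so of the two columns only EoT can show a finding.

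7. **Laboratory comparison.** SAP 2.7.3 tabulates laboratory values by worst post-baseline grade and worst on-treatment shift, which does not depend on the planned visit. The ECG table has no such line.

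8. **Reader.** The SAP says central and the protocol says local. SAP section 4 lists the changes to protocol-specified analyses and has no entry for ECGs.

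**The case against.** The strongest reply is that the SAP does not use the word only. Its general rule places all unscheduled assessments in abnormality tables, and the triplicate sentence presupposes that such ECGs are analysed. On that reading nothing is lost. This stands to the extent that omission is a risk and not a certainty. It does not remove the conflict, because the by-visit rule in the same section says the opposite.

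There are also other routes. Protocol 8.3.5.1 sends new or worsened clinically significant ECG findings to the AE page, and so to the adverse event tables. SAP 2.1 lists unscheduled assessments. Both stand, but they are partial. A change that crosses a numerical threshold and is judged not clinically significant need not become an adverse event, and a listing gives no count.

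A third reply is that this is descriptive output in a single-arm study, no decision depends on it, and Protocol 4.5 reports no clinically relevant QT effect to date. That limits the weight of the point. It does not justify leaving two instructions in conflict.

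A reader might also infer from the SAP that the limits on uncorrected QT are an error, or that site machines may have supplied differently corrected values. The documents do not support either. QT and QTcF are separate named parameters, so tabulating both is a choice that leaves the QTcF result intact, and both documents name Fridericia-corrected QT.

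**Conclusion.** The SAP contradicts itself on whether unscheduled ECGs enter the notable-value table, and its specific sentence is narrower than the protocol's. For-cause ECGs taken on treatment may therefore be missing from the count. The screening column is uninformative. The central-versus-local statement is an unrecorded contradiction of the protocol.

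The size cannot be expressed as a number of subjects or a percentage. The documents do not say how many unscheduled ECGs were taken, and the number could be zero. What can be said is structural: 14 infusion visits with no scheduled ECG and one scheduled post-baseline ECG, for a subject who completes dosing. A subject who stops early has an EoT visit within 14 days of the last dose, or at a regular visit that serves as EoT (Protocol 9.1.1), so a scheduled ECG can then fall within the planned dosing weeks.

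A reader might infer that all QT findings on drug disappear from the table. They do not, because the EoT tracing is on-treatment and is counted. A reader might also link the reader statement to lost values. It removes none and is a documentation error only.

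**What to change.** In SAP 2.7.4.1, replace the visit-based sentence with: *number and percentage of subjects with at least one notable post-baseline value at any on-treatment ECG, scheduled or unscheduled, among subjects with a baseline and at least one post-baseline ECG*. An EoT column may be shown in addition, and the screening column can go. This follows the abnormality-table rule in SAP 2.1 and matches the treatment of laboratory data in SAP 2.7.3.

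In the same section, change centrally to locally, in line with Protocol 12.6.2.

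The cost is SAP wording and a small programming change. No new data are needed. The drawback is that unscheduled ECGs are taken for cause, so the percentage may rise slightly and is not comparable with one from scheduled tracings alone. A footnote saying so is enough.

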2.7.4.2 Vital signs

Vital sign assessments are performed in order to characterize basic body function. The following parameters were collected: weight (kg), body temperature (°C), pulse rate (beats per minute), systolic and diastolic blood pressure (mmHg), respiratory rate and oxygen saturation.

Vital signs collected on-treatment will be summarized descriptively. Values measured during pre- and post- treatment period will be flagged in listings.

The number and percentage of subjects with notable vital sign values will be presented over time. Notable values will be flagged in the listings. For analysis, clinically notable vital sign criteria are provided in Table 2-2 below:

Table 2-2 Clinically notable changes in vital signs

Vital sign (unit)	Criteria	< 18 years at baseline and < 18 years at time of assessment	< 18 years at baseline and ≥ 18 years at time of assessment	≥ 18 years at baseline
Systolic blood pressure (mmHg)	High	≥ 95th percentile of the age and height group ¹	≥ 180 with increase from updated baseline ⁵ of ≥20	≥180 with increase from baseline of ≥20
	Low	≤ 5th percentile of the age and height group ¹	≤ 90 with decrease from updated baseline ⁵ of ≥20	≤90 with decrease from baseline of ≥20

Vital sign (unit)	Criteria	< 18 years at baseline and < 18 years at time of assessment	< 18 years at baseline and ≥ 18 years at time of assessment	≥ 18 years at baseline
Diastolic blood pressure (mmHg)	High	≥ 95th percentile of the age and height group ¹	≥ 105 with increase from updated baseline ⁵ of ≥15	≥105 with increase from baseline of ≥15
	Low	≤ 5th percentile of the age and height group ¹	≤ 50 with decrease from updated baseline ⁵ of ≥15	≤50 with decrease from baseline of ≥15
Pulse rate (bpm)	High	12-15 years: >96 ≥15 years: >92	≥120 with increase from updated baseline ⁵ of ≥15	≥100 with increase from baseline of >25%
	Low	12-15 years: <62 ≥15 years: <58	≤50 with decrease from updated baseline ⁵ of ≥15	≤50 with decrease from baseline of >25%
Weight (kg)	High	increase from baseline ³ of ≥2 BMI-for-age percentile categories ⁴	increase from updated baseline ⁵ of ≥10%	increase >10% from baseline
	Low	decrease from baseline ³ of ≥2 BMI-for-age percentile categories ⁴	decrease from updated baseline ⁵ of ≥10%	decrease >10% from baseline
Respiratory rate (breath per minute) ^{2,6,7}	High	12-15 years: >21 ≥15 years: >20	≥30	≥30
	Low	12-15 years: < 15 ≥15 years: <13	≤10	≤10
Oral body temperature (°C)	High	≥38.4	≥39.1	≥39.1
	Low	≤35.0	≤35.0	≤35.0

bpm=beats per minute; NHLBI= National Heart, Lung, and Blood Institute;

¹ Blood pressure percentiles are calculated for each blood pressure record using the method described in Appendix B of the following reference: The Fourth Report on Diagnosis, Evaluation and Treatment of High Blood Pressure in Children and Adolescents. Pediatrics 2004; 114; 555.

² Fleming S, 2011

³ Baseline BMI-for-age weight status categories are underweight (less than the 5th percentile), healthy weight (5th percentile to less than the 85th percentile), overweight (85th to less than the 95th percentile) and obese (equal to or greater than the 95th percentile);

⁴ BMI-for-age percentiles categories (P3, P5, P10, P25, P50, P75, P85, P90, P95, P97) are obtained from the WHO Growth Charts;

⁵ Updated baseline is the last value collected before the 18th birthday.

⁶ Eldridge L, 2014;

[figure not shown]
⁷ Kou R, 2009.

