**Table 8-3 Physical assessments**

Assessment	Specification
Physical examination	
A complete physical examination will include the examination of general appearance, skin, neck (including thyroid), eyes, ears, nose, throat, lungs, heart, abdomen, back, lymph nodes, extremities, vascular, and neurological. If indicated based on medical history and/or symptoms, rectal, external genitalia, breast, and pelvic exams will be performed. A complete physical examination will be performed at screening and within 7 days following last infusion.
 
An abbreviated (short) physical exam will include the examination of general appearance and vital signs (blood pressure [BP] and pulse), as well as additional components of the physical exam, as needed based on observed signs or reported symptoms. A short physical exam will be performed at all visits for which there is a scheduled study drug infusion.
 
Significant findings that were present prior to the signing of informed consent must be included in the Medical History page on the subject's CRF. Significant new findings that begin or worsen after informed consent must be recorded on the Adverse Event page of the subject's CRF.

Vital sign	Vital signs include blood pressure (supine position preferred when ECG is collected), pulse measurement, respiratory rate, oxygen saturation, and body temperature will be measured as specified in Table 8-1 .
Height and weight	
Height in centimeters (cm) will be measured at screening.
 
Body weight (to the nearest 0.1 kilogram (kg) in indoor clothing, but without shoes) will be measured at screening and all visits for which there is a scheduled study drug infusion (for dosing), as specified in Table 8-1.

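### SAP Table 2-2's adolescent vital-sign rules overlap at age 15, change the baseline and high-pulse rule at the 18th birthday, and need a height that is taken only once

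*SAP*

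**What the plan says.** SAP 2.7.4.2 will tabulate subjects with notable vital signs over time and flag the values in listings, using Table 2-2. The table has three columns: under 18 at both baseline and assessment; under 18 at baseline but 18 or over at assessment; and 18 or over at baseline.

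- **Age bands (first column).** High pulse is "12-15 years: >96 ≥15 years: >92" and low pulse "12-15 years: <62 ≥15 years: <58". High respiratory rate is "12-15 years: >21 ≥15 years: >20" and low "12-15 years: < 15 ≥15 years: <13".
- **Turning 18 (second column).** Change is measured from an updated baseline, defined in footnote 5: "Updated baseline is the last value collected before the 18th birthday". SAP 2.1.1 defines the general safety baseline as the last assessment on or before the start of treatment.
- **High pulse from age 18.** The second column requires at least 120 bpm with a rise of at least 15 bpm. The third requires at least 100 bpm with a rise of more than 25%.
- **Weight (first column).** The rule is a shift of at least two BMI-for-age percentile categories from baseline. Footnote 3, attached to the word baseline, begins "Baseline BMI-for-age weight status categories are underweight (less than the 5th percentile), healthy weight (5th percentile to less than the 85th percentile" and goes on to overweight and obese. Footnote 4, attached to the word categories, says "BMI-for-age percentiles categories (P3, P5, P10, P25, P50, P75, P85, P90, P95, P97) are obtained from the WHO Growth Charts".
- **Blood pressure (first column).** Limits are percentiles for age and height, calculated for each record.
- **Height.** Protocol Table 8-3 says "Height in centimeters (cm) will be measured at screening", and Protocol Table 8-1 marks it once, at the third screening visit. Weight is taken at screening and at every infusion visit.

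**The concern.** A flagging table has to give one answer for each measurement, and the answer should mean the same thing for subjects of the same age. Table 2-2 falls short in four places: a shared boundary at 15, a reference value that can move onto treatment at the 18th birthday, two high-pulse rules for people who are all 18 or over when measured, and height-based percentiles with no current height. Where the text gives two answers, the programmer picks one. Where it gives one, that answer may not describe change since before drug. At stake are the counts and listing flags of notable vital signs in the youngest subjects, for whom the trial has the least safety information.

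**Working it through.** The plan states no figure to reproduce. Each rule is applied as written.

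**1. Age 15.** Whole-number values on which the two bands disagree:

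| Criterion | 12-15 band | 15-and-over band | Values in dispute |
|---|---|---|---|
| Pulse high | >96 | >92 | 93, 94, 95, 96 |
| Pulse low | <62 | <58 | 58, 59, 60, 61 |
| Respiratory rate high | >21 | >20 | 21 |
| Respiratory rate low | <15 | <13 | 13, 14 |

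Reach: the minimum age was 16 until Amendment 2, when 25 subjects were enrolled, and the final total was 36. At most 36 - 25 = 11 could have entered at 12-15.

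**2. Baseline after the 18th birthday.** Infusion visits, with vital signs, fall on Days 1, 15, 43 and every 28 days to 351 (14 visits). Take birthdays on Days 2 to 351, which is 350 days, with all visits on schedule. A birthday on Days 2-15 leaves the Day 1 or earlier value as the last before it. From Day 16 on, the last value is post-first-dose: 351 - 16 + 1 = 336 of 350 days (96%).

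Two invented pulse sequences show the consequence:

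- *Low pulse:* 76 before drug, 60 at the last visit aged 17, 50 after the birthday. The 60 is not below 58, so it is not flagged at 17. The later 50 meets the limit of 50 or less but is only 60 - 50 = 10 below the updated baseline, short of the required 15, so it is not flagged either. From the SAP 2.1.1 baseline the fall is 76 - 50 = 26 and would be flagged.
- *High pulse:* 76, then 108 at 17, then 122 at 18. The last value is 122 - 76 = 46 above the pre-treatment value but 122 - 108 = 14 above the updated one, so it is not flagged. Here the 108 was already flagged at 17 (>92). This holds in general: a value of 120 or more escapes the 15 bpm criterion only if the updated baseline exceeds 120 - 15 = 105, which is above 92.

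Respiratory rate and temperature have no change criterion after the birthday, so footnote 5 does not affect them.

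**3. High pulse from age 18.** For 76 to 100 bpm, 100/76 - 1 = 31.6%. A subject who entered at 18 is notable (at least 100, rise above 25%). One who turned 18 on study is not (below 120). The latter's 100 bpm was notable while he was 17 (>92) and stops being so at the birthday.

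**4. Weight categories and height.** A move from the 45th to the 76th percentile crosses two of footnote 4's categories (P25-P50 to P75-P85) but none of footnote 3's, since both values are healthy weight.

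With height frozen at screening, BMI is overstated by (1 + growth/height)² - 1. Growth is not in the documents. Assuming 0 to 8 cm over the year from 150 cm:

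- 0 cm: 0%
- 4 cm: (154/150)² - 1 = 5.4%
- 8 cm: (158/150)² - 1 = 11.0%

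For screening heights of 145 to 170 cm, the 8 cm figure runs from 11.3% down to 9.6%. The error always favours a high shift and can mask a low one. How many categories it moves a subject cannot be computed, because the growth charts are not in the documents.

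**The case against.** Several replies have force.

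- The first band may be meant as 12 to under 15. That would remove the overlap, but no text says so.
- Footnote 5 is an explicit, named convention, so it does not contradict anything within Table 2-2. This stands: the complaint is that it departs from SAP 2.1.1 and moves the reference onto treatment.
- A reader might infer that any change on drug is wiped out at the birthday. The documents do not support that. Until then the first column applies at every visit, and values crossing its limits are counted and listed. What can go unflagged is drift that stayed within those limits, as in the low-pulse sequence.
- A reader might also infer that a 17-year-old going from 76 to 100 bpm is never notable. He is, until he turns 18.
- A reader might place all of this in the age group added by Amendment 2. Treatment lasts at most 52 weeks, so someone entering at 12-15 cannot turn 18 on it. The birthday rules concern subjects aged 16 or 17 at entry, who were eligible from the start.
- Footnotes 3 and 4 might look irreconcilable. They are not: footnote 3's boundaries (P5, P85, P95) are all among footnote 4's cut points, and a baseline percentile can be placed on footnote 4's scale. The wording leaves the choice open, but the count is feasible.
- It is tempting to say that weight gain will be over-reported. Only a BMI error under assumed growth is shown; no shift of two categories is.

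**Conclusion.** The point holds as a minor one. The age-15 overlap is a real ambiguity in pulse and respiratory limits, affecting at most 11 subjects. The birthday rule usually replaces a pre-treatment reference with a post-first-dose one (336 of 350 birthday days, assuming visits on schedule) and can leave gradual change unflagged. The two high-pulse rules treat subjects of the same age differently. The two category sets leave the weight count open. The missing later heights bias adolescent weight flags towards high by an amount that depends on growth and cannot be sized from the documents; blood pressure percentiles have the same gap. It would be too strong to conclude that the trial's safety assessment is unsound: these are descriptive flags with no test attached, and neither the primary endpoint nor the sample size is affected.

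**What to change.** Edit SAP Table 2-2 and its footnotes:

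1. Make the pulse and respiratory bands non-overlapping at 15.
2. Use the SAP 2.1.1 pre-treatment baseline for change criteria after the 18th birthday, or report it beside the updated one.
3. Reconcile the two high-pulse rules so that one applies to everyone aged 18 or over at assessment. The sponsor's clinicians should choose the limits.
4. Count weight shifts, baseline included, on footnote 4's categories only.
5. State that later BMI and blood pressure percentiles use the screening height, and record the bias towards high weight flags as a limitation.

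Percent weight change should not replace the BMI rule in growing subjects: a boy going from 150 to 158 cm at constant BMI gains (158/150)² - 1 = 11.0% in weight and would pass a 10% limit through growth alone.

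The cost is a table edit and the matching programming, with no new data collection.
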